### D.5. Follow-up Clinic Visits and Phone Calls

Follow-up clinic visits will be conducted when subjects are in stable clinical status, where at least 2 weeks have elapsed since the time of their last prednisone or antibiotic course for treatment of a COPD exacerbation. Participants in both arms will be seen in our research clinics at months 3, 6, and 12 (Table 5). At each follow-up visit, study staff will remind participants not to disclose treatment arm. Subjects will be reminded that they should be working to slowly and steadily increase their walking and exercise. Subjects will perform 6MWT, spirometry, and HRQL assessments. All changes in medication or clinical status will be noted, any potential adverse events recorded, and a history of any COPD exacerbations or hospitalizations in the previous 3 months ascertained. We will also assess dyspnea (UCSD Shortness of Breath Questionnaire and MMRC Scale), physical activity (CHAMPS and [name]), and depression (Beck Depression Inventory). Subjects will also complete the following questionnaires: the Barriers to Exercise, Physical Activity Recall, VR-36, MOS Social Support, Bristol's COPD Knowledge, Exercise Self-Efficacy, Epworth Sleepiness Scale, the Brief Pain Inventory (short form, administered at C03, C06 and C12), and the Dietary Questionnaire (only administered at C00 and C12). The intervention subjects will also complete the Intervention Feedback Questionnaire that asks about the subject's experience with the study website and pedometer at the 6-month and 12-month in-clinic study visits. Blood for inflammatory biomarkers will be drawn by venipuncture, packed in a shipping container with an ice pack, and transported to the MAVERIC blood lab for processing and storage. Subjects recruited at VA Boston will be asked to complete DXA scans for body composition and bone mineral density at the 12-month in-clinic visit, and additionally will be asked to complete a body composition measurement using the Omron HBF-306CN. We will exclude any subject with a pacemaker or defibrillator to minimize any potential risks. If subject has previously undergone a DXA scan at the VA Boston Osteoporosis Clinic within 6 months, then the data from the Osteoporosis Clinic may be used and subject does not need to complete a scan specifically for the research study. If a subject does not complete the study-related questionnaires during the in-clinic visit, research staff will contact the subject after study visit by phone to finish the questionnaires over the phone or send the questionnaires home with the subject to be completed and returned in a pre-paid mailer.

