
To objectively measure engagement in PA, the pedometer will directly measure 14 days of walking of subjects in both arms. To assess treatment fidelity, exercise logs will be collected from subjects each month. Participants will be contacted by telephone at month 9. They will provide an interim history of home exercise and answer questions about symptoms, medications, AEs, and hospitalizations that occurred during the prior 3 months. Subjects will also receive a mailing with questionnaires (Barriers to Exercise, Physical Activity Recall, SGRQ, VR-36, UCSD SOB, Bristol's COPD Knowledge, Exercise Self-Efficacy, CHAMPS Physical Activity, Beck Depression Inventory, and Exercise Logs) to complete at home. At any time, if a subject experiences a medical problem that prevents walking and exercise, s/he will be suspended from the study. S/he will resume the study when s/he has returned to baseline clinical status.

It is expected that some subjects may be unable to complete all the proposed assessments during the study visits. Furthermore, subjects may refuse to complete any portion of the study assessments.

**Table 5:** Schedule of Clinic Visits (C), Telephone Calls (P), and Assessments (both study arms)

	Baseline C00	Month 3 C03	Month 6 C06	Month 9 P09	Month 12 C12
Medical and Exercise History	X	X	X	X	X
6-Minute Walk Test	X	X	X		X
Barriers to Exercise Questionnaire	X	X	X	X	X
Physical Activity Recall Questionnaire	X	X	X	X	X
HRQL SGRQ	X	X	X	X	X

Veterans SF-36 HRQL	X	X	X	X	X
MOS Social Support Questionnaire	X	X	X		X
MMRC	X	X	X		X
UCSD SOB	X	X	X	X	X
Spirometry	X	X	X		X
Blood Draw for Biomarkers	X	X	X		X
Beck Depression Inventory	X	X	X	X	X
CHAMPS Physical Activity Questionnaires	X	X	X	X	X
Bristol's COPD Knowledge	X	X	X	X	X
Exercise Self Efficacy	X	X	X	X	X
Epworth Sleepiness Scale	X	X	X		X
Brief Pain Inventory (Short form)	X	X	X		X
Intervention Feedback Questionnaire (Intervention arm only)			X		X
Dietary Questionnaire	X				X
Exacerbation, Adverse Event Monitoring, and Hospitalization History	X	X	X	X	X
Daily Exercise Logs	X	X	X	X	X
Daily Step Count	X	X	X	X	X
DXA Scan (VABoston site only)*	X				X
Body Composition/Bioimpedance (VABoston site only)	X**				X**

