### **Monitoring for Adverse Events (AdEs)**

We have convened an independent, external Data and Safety Monitoring Board (DSMB) to review recruitment, follow-up rates, protocol adherence, and safety results. The DSMB is composed of [name], an expert in pulmonary rehabilitation and COPD clinical trials and pulmonologist at Boston Medical Center, [name]. an expert in telemedicine methods in COPD at Southern California Kaiser Permanente, and [name], PhD, NP an expert in patient-centered coaching and behavioral change methodologies and interventions in persons with COPD at Touro University of California. They will meet every 6 months, and as needed, by telephone conference. They will monitor the number of adverse events (AdEs) and serious adverse events (SAEs) and unanticipated problems between the 2 arms of the study.

Although the proposed study presents minimal risk, there is the potential for AdEs related to increased walking and exercise. Based upon our pilot study with ESC, the most common SAE will be hospitalizations for a COPD exacerbation, which are unrelated to the exercise intervention.

The most common AdEs will be musculoskeletal injuries. In order to minimize risk, subjects will be enrolled in the study only if they have medical clearance from their healthcare provider. In addition, subjects will be screened for clinically active cardiovascular disease (such as angina or decompensated congestive heart failure) and exercise-induced hypoxemia as part of baseline testing. Subjects in both arms will be instructed to notify their healthcare provider if they experience any change in their clinical condition, and to notify study staff of any change in medications, urgent care visits, emergency room visits, or hospitalizations. During the study, subjects will be regularly monitored for adverse effects of exercise during clinic visits and telephone contacts. In addition, participants can report adverse events (AdEs) by telephone at any time. The PI will contact participants by telephone if any reported AdE suggests clinical deterioration warranting immediate medical attention. All SAEs and unanticipated problems will be reported to the respective IRBs at the time of continuing review, but would be reported to the study DSMB immediately. If an event is possibly, probably or definitely related to the intervention, it will be classified as intervention-related.

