**Table 2. Summary of Key Study Design Features to Ensure Internal and External Validity**

Eligibility Criteria	Randomization	Treatment Fidelity	Missing Data
>90% pedometer accuracy	Unpredictable Blocks	Track with daily exercise logs and enhance with every 3 month follow-ups	Most common cause of missing data (health reasons) will be same for both arms
Able to collect $\geq 5$ of 10 days of valid baseline step count data	Allocation Concealment	Lack of treatment fidelity defined a priori as <70% days with exercise	Impute with least favorable value or carry forward previous values
	Blinding of RAs performing assessments	Sensitivity analysis accounting for treatment fidelity	Sensitivity analysis excluding subjects with missing data

The most important factor affecting compliance is the complexity of the intervention. Our experience indicates that the WEB program and pedometer intervention pose minimal participant burden. The WEB intervention is designed to foster compliance, using a dynamic website and immediate feedback. Subjects upload step counts and visit the website at their convenience. ESC, a similar study, has shown persistent engagement by participants at month 3, and similar retention and engagement has been shown at month 12 in a separate study. Our preliminary

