Based on our previous work, medical problems and temporary suspension from the exercise program will be the most common reason for missing outcomes data in both arms. We have designed the testing windows to minimize missing data. At months 3 and 6, testing will be allowed within a window of  $\pm 2$  weeks. At months 9 and 12, testing will be allowed within a window of  $\pm 1$  month, making the total participation time up to 13 months from the baseline in-clinic study visit (C00). Despite our efforts at follow-up, some missing data are expected with multiple testing visits. We will collect the reasons for missing data such as death, COPD exacerbation, medical reasons, or non-medical reasons. We will compare the rate of losses to follow-up at 3, 6, 9, and 12 months among the two arms using the chi-square test of association. We will assess whether any baseline characteristics such as age, FEV1 % predicted, or 6MWT distance, are associated with losses to follow-up using chi-square tests for categorical baseline data and analysis of variance for continuous baseline data. If baseline variables and treatment group are found to be associated with loss to follow-up, then the analysis models will be modified to include the differing baseline variables as covariates to provide unbiased estimates of intervention effects. For subjects who discontinue the study early due to worsening of COPD or due to death, missing outcome data will be imputed using the least favorable data observed prior to discontinuation. Missing data for subjects who miss a visit not related to worsening of COPD will be imputed using last observed data. We will also perform sensitivity analyses using the complete case method, excluding those with no observed outcome at 6 months.

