During the study, subjects will be regularly monitored for adverse effects of exercise during clinic visits and telephone contacts. In addition, participants can report adverse events (AdEs) by telephone at any time. The PI will contact participants by telephone if any reported AdE suggests clinical deterioration warranting immediate medical attention. Subjects in both arms will be instructed to notify study staff if they experience any change in their clinical condition, any change in medications, or have urgent care visits, emergency room visits, or hospitalizations. During the study, if a subject experiences a medical problem that prevents walking and exercise, he will be temporarily suspended from the study and will resume when at baseline clinical status. Any AdEs that are immediately life-threatening, cause permanent or lasting harm, or require a hospitalization will receive a serious classification. All serious adverse events (SAE) and unanticipated problems will be reported to the respective IRB at continuing review but reported to the study DSMB immediately. If an event is possibly, probably or definitely related to the intervention, it will be classified as intervention-related. Based upon our prior experience, the most common SAE will be hospitalization for a COPD exacerbation. The most common AdE will be musculoskeletal injuries.

We have convened an independent, external Data and Safety Monitoring Board (DSMB). They will monitor the rates of AdEs and SAEs and unanticipated problems between the 2 arms of the study. The DSMB is composed of [name] an expert in pulmonary rehabilitation and COPD clinical trials at Boston Medical Center, [name] an expert in telemedicine methods in COPD at Southern California Kaiser Permanente, and [name], PhD, NP an expert in patient-centered coaching and behavioral change methodologies and

interventions in persons with COPD at Touro University of California. They will meet every 6 months, and as needed, by telephone conference.

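### The suspension rule can stop outcome collection in subjects who have not recovered, and the planned missing-data handling does not record their deterioration

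*Combined protocol and SAP*

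**What the plan says.** All references are to the combined protocol and SAP.

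- **Section D.5, follow-up visits and calls:** "At any time, if a subject experiences a medical problem that prevents walking and exercise, s/he will be suspended from the study". On return: "S/he will resume the study when s/he has returned to baseline clinical status". There is no time limit, no definition of baseline clinical status, and no rule for a subject who never regains it.
- **Human Studies Section, (2)(b) Protection Against Risks:** the rule is repeated, with a qualifier: "he will be temporarily suspended from the study and will resume when at baseline clinical status".
- **Minimizing Attrition and Handling Missing Data:** "medical problems and temporary suspension from the exercise program will be the most common reason for missing outcomes data in both arms". Here it is the exercise program that is suspended.
- **Visit timing:** D.5 states "Follow-up clinic visits will be conducted when subjects are in stable clinical status", meaning at least two weeks after the last prednisone or antibiotic course for an exacerbation. The attrition section adds "At months 3 and 6, testing will be allowed within a window of" plus or minus 2 weeks.
- **Missing-data rules (attrition section):** after early discontinuation for COPD worsening or death, the least favorable earlier value is used. For a missed visit unrelated to COPD worsening, the last value is carried forward. A complete-case sensitivity analysis excludes subjects with no 6-month outcome.
- **Table 2:** "Most common cause of missing data (health reasons) will be same for both arms".

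**The concern.** Being suspended from a study and pausing an exercise program are different things. The first can be taken to end visits and measurements as well as exercise; the second leaves measurement in place. D.5 is the section that staff would follow for visits, and it uses the wider wording.

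Return is conditional on recovery. If assessments stop during suspension, the subjects who go unmeasured at month 6 are those who have not recovered. That is selection on health after randomization, which the intervention may itself change. Adjusting for baseline covariates, as the attrition section proposes, does not remove it. The comparison most exposed is the primary one, 6MWT distance at 6 months.

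Table 2 sets the issue aside by stating that health-related missingness will be alike in the two arms, but no data are given for that. The adverse-event section says "there is the potential for AdEs related to increased walking and exercise", and the aims hypothesize fewer exacerbations and COPD-related hospitalizations under the intervention (WEB). Either could make the arms differ.

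**Working it through.** **1. What is suspended.** D.5 and Protection Against Risks say the study; the attrition section says the exercise program. No section says which assessments continue. The attrition section does link suspension to lost outcome data, so the authors expect some loss.

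**2. A suspended subject at month 6.** Someone not back at baseline status, or not yet stable, when the 2-week window closes has no month-6 6MWT.

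- *Discontinued for COPD worsening:* the worst earlier 6MWT (baseline or month 3) is used.
- *Missed visit for another reason, such as a walking injury:* the last earlier 6MWT is used.
- *Suspended for COPD worsening but not discontinued:* read literally, neither rule covers this case.
- *Complete-case sensitivity analysis:* the subject is dropped.

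The imputed values all predate the event, and the sensitivity analysis removes the subject. Neither shows the deterioration.

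**3. The plan's own figure.** Inputs (power calculation): difference 54 m, SD 100 m, power 80%, alpha 0.05 (taken as two-sided), 40% drop-out.

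- Normal approximation: n = 2 × [100 × (1.960 + 0.842) / 54]² = 53.8, so 54 per arm.
- Two-sample t-test: 54.8, so 55 per arm, with power 80.1%.
- Total: 111 / 0.60 = 185.

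The sample size reproduces. The drop-out allowance protects precision; it does nothing about who is missing. Retaining subjects would also add power: 81.2% at 40% missing against 90.7% at 20% missing (185 randomized, normal approximation).

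**4. Possible size of the bias.** Let p be the share of an arm whose month-6 value is replaced by a pre-event value, and L the average loss in metres that goes unrecorded. Then

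bias (WEB − control) = p_WEB × L_WEB − p_control × L_control,

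or (p_WEB − p_control) × L if the losses are equal. The complete-case contrast has the same form, with L read as the shortfall of suspended subjects relative to the others. The documents give neither p nor L, so these inputs are assumptions:

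| Difference in p | L = 54 m | L = 100 m |
|---|---|---|
| 0 points | 0 m | 0 m |
| 5 points | 2.7 m | 5.0 m |
| 10 points | 5.4 m | 10.0 m |

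The non-zero range is 2.7/54 = 5% to 10/54 = 19% of the target difference. If the true difference is zero and the SD is 100 m, the standard error is 100 × √(2/55.5) = 19.0 m with 55.5 per arm and 100 × √(2/92.5) = 14.7 m with 92.5 per arm. The two-sided 5% test then rejects in 5.2–5.4% of trials at 2.7 m of bias, 5.9–6.6% at 5.4 m, and 8.2–10.4% at 10 m. More suspensions on WEB would favor WEB; more in control would work against it.

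**5. Event outcomes.** Section D.6 captures exacerbations and hospitalizations by self-report, calls to staff and chart review, and asks at each visit about hospitalizations since the previous one. A returning subject's suspended period is therefore largely covered. The gap is the subject who never returns: patient report prompts the records request, and the event model sums over 12 months with no listed adjustment for time observed.

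**The case against.** The strongest reply is that this is a wording slip. No section says measurement stops, Protection Against Risks calls the suspension temporary, and the attrition section names the exercise program. A reader might infer that the trial stops measuring everyone who deteriorates and so cannot give an intention-to-treat answer. The documents do not support that. All subjects are analyzed as randomized, missing values are imputed, reasons for missingness are collected and losses are compared by arm. A subject who recovers within the window is measured. What stands against the reply is that no section secures assessment during suspension, and that the safeguards detect loss or fill it with earlier values. The mixed model's flexibility with missing data helps little here: the primary model uses baseline and month 6 only, so without imputation a suspended subject contributes just the baseline value.

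A reader might also infer a high trigger rate from the expected 106 exacerbations in 111 subjects over 12 months. That is 0.955 per year, or 1 − exp(−0.4775) = 38% with at least one in six months under a Poisson model. This is not a suspension rate. Suspension needs a problem that prevents walking, and the plan foresees sick weeks met simply by a lower step goal. Overdispersion, which the planned negative binomial model allows for, would also lower the 38%.

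Nor can it be inferred that subjects left worse never return. Baseline clinical status is undefined, and the visit criterion is two weeks since treatment.

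Finally, different missingness by arm is plausible but not shown. Both arms are told to increase walking, so injury risk is not confined to WEB, and more injuries could offset fewer exacerbations. This stands. It also means that Table 2's statement of equality is unproven, and equal rates would still leave bias if the unrecorded losses differed.

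**Conclusion.** The concern holds as a risk of bias in the intention-to-treat comparison, not as a failure to deliver one. The sections conflict on what is suspended and none keeps suspended subjects in outcome follow-up. Followed as D.5 and Protection Against Risks are worded, month-6 6MWT data can be lost selectively in subjects who have not recovered. The planned imputation and the complete-case analysis would not reveal that loss.

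Size and direction are unknown, because the documents give no suspension rate. The 2.7 to 10 m illustration rests on an assumed 5 to 10 point difference between arms and an assumed equal unrecorded loss of 54 to 100 m; with equal rates and equal losses it is zero. The exposure lies mainly in the clinic measures, above all the 6MWT. Event outcomes are largely protected, except in subjects who never return.

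**What to change.** 1. Reconcile D.5 and Protection Against Risks with the attrition section on what is suspended. When exercise pauses and resumes stays with the investigator.
2. State that suspended subjects remain in outcome follow-up. Questionnaires and the exacerbation and hospitalization history continue on schedule by phone or mail, routes the plan already uses. The 6MWT and blood draw are taken at the first visit that the existing stability rule (D.5) and walk-test safety rules (D.6) allow. Blood should not be drawn on schedule during acute illness, because that would conflict with the stability rule and could distort CRP and IL-6.
3. Record the actual date of each 6MWT. Set in advance an upper limit for a late test to count as month 6, since an unlimited delay would run well into the maintenance phase. Add an in-window-only sensitivity analysis.
4. Add a sensitivity analysis for subjects unable to walk at month 6 that does not rely on pre-event values. Options are to rank them below all measured distances, or to subtract a range of losses (for example 0, 54 and 100 m) from imputed values separately by arm. Name the missing-data rule for a subject who is suspended for COPD worsening but has not discontinued.
5. Report the number, reason and duration of suspensions by arm, and delete the Table 2 statement of equal health-related missingness.

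The cost is protocol wording, slightly less uniform month-6 timing and a little more analysis work.

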**Secondary Outcomes:**

**a. HRQL:** Respiratory-specific HRQL will be assessed with the SGRQ (82,92). We will examine the composite Total Score as well as the subscales of Activity, Symptoms, and Impact. Lower SGRQ scores indicate better health status. The SGRQ has been validated and used extensively in assessments of HRQL in COPD (82,92).

The Veterans' SF-36 questionnaire will be used to assess general health status.

**b. Dyspnea** (Appendix 2): Dyspnea will be quantified with the UCSD Shortness of Breath Questionnaire (93) which has been widely used in COPD research. The minimal clinically important change has been determined to be  $\pm 5$  units (94). Dyspnea will also be assessed using the MMRC scale (responses 0-4 with 4 being the most dyspneic) which is used to calculate the BODE index (81, 91).

**c. Markers of Systemic Inflammation:** Blood will be collected by venipuncture in three 10 mL purple top EDTA tubes. Samples from both study sites will be shipped to MAVERIC for processing and storage. Samples will be centrifuged and the plasma isolated. Plasma will be stored in 1 mL aliquots and frozen at  $-80^{\circ}\text{C}$ . For the analysis of CRP and IL-6, aliquots will be sent to the Clinical & Epidemiologic Research Laboratory, Department of Laboratory Medicine at Children's Hospital in Boston, a state-of-the-art laboratory that specializes in micro-analysis and is dedicated to testing for research studies. This laboratory has performed our previous CRP and IL-6 analyses, and these assays are standardized and highly reproducible.

C-Reactive Protein (CRP): The concentration of CRP will be determined using an immunoturbidimetric assay on the Hitachi 917 analyzer (Roche Diagnostics, Indianapolis, IN), using reagents and calibrators from Denka Seiken (Niigata, Japan). In this high sensitivity assay, an antigen-antibody reaction occurs between CRP in the sample and an anti-CRP antibody that has been sensitized to latex particles, and agglutination results. This antigen-antibody complex causes an increase in light scattering, which is detected spectrophotometrically, with the magnitude of the change being proportional to the concentration of CRP in the sample. This assay has a sensitivity of 0.03 mg/L. The day-to-day variability of the assay at concentrations of 0.91, 3.07 and 13.38 mg/L are 2.8, 1.6 and 1.1%, respectively.

Interleukin-6 (IL-6): IL-6 is measured by an ultra-sensitive ELISA assay from R & D Systems (Minneapolis, MN). The assay employs the quantitative sandwich enzyme immune assay technique. A monoclonal antibody specific for IL-6 has been pre-coated onto a microtitre plate. After the samples, standards, controls and conjugates are added to the wells, IL-6 is sandwiched between the immobilized antibody and the enzyme-linked antibody specific to IL-6. Upon the addition of substrate, a color is generated that is proportional to the amount of IL-6 present in the sample. The minimum required volume for this assay is 200  $\mu\text{L}$ . The assay has a sensitivity of 0.094 pg/mL, and the day-to-day variabilities of the assay at concentrations of 0.66, 1.97 and 8.16 pg/mL are 12.2%, 7.6%, and 9.9%, respectively.

**d. Acute Exacerbation and Hospitalization History:** Assessment of AEs and COPD-related hospitalizations is based on both self-report and medical chart review. During the study, all subjects will be instructed to call study staff with any changes in clinical status or medications. Most patients remember the occurrence of AEs because they are well-defined periods of worsening symptoms that require treatment with an antibiotic and/or prednisone (83). At clinic

visits and telephone contacts, study staff will assess changes in symptoms, changes in medications, prednisone and antibiotic use, visits to the emergency room, and hospitalizations. At each study visit, participants will be asked to provide the dates and locations of all hospitalizations since the previous visit. Patient report will prompt study staff to request hospital discharge summaries, medication records, chest X-ray reports, CT scan reports, and any additional information. Patient reports will be verified with review of hospitalization and pharmacy records both in and outside VA facilities, whenever possible. [name] major role on the project is to adjudicate the clinical events during the study. He will have no involvement in the day-to-day conduct of the study and will be blinded to subjects' treatment assignment and baseline test results. He will review subject responses and all medical records to determine if an AE or COPD-related hospitalization has occurred. An AE will be clearly defined as "a complex of respiratory symptoms (increased or new onset) of more than one of the following: cough, sputum, wheezing, dyspnea, or chest tightness with a duration of at least 3 days, requiring treatment with antibiotics or systemic steroids" (84). Occurrence of AEs within 14 days of each other will be considered a single AE (85,86). This definition will also be used at the baseline visit for assessment of occurrence of AEs in the year prior to study entry.

**e. Daily Step Count:** A secondary outcome, daily step count will be used to directly measure engagement in PA in both arms. To measure baseline step count, subjects will be instructed to wear the pedometer attached to a belt or garment waistband during all waking hours except when showering/bathing for 14 days. They will be instructed to perform their usual physical activities and exercise. Subjects will be instructed to remove the pedometer at night and put it in a place where they will remember to wear it first thing in the morning, such as with their alarm clock, watch, eyeglasses, or breathing medicines. The pedometer will have a sticker covering the digital display to prevent feedback. After randomization, the pedometer is part of the WEB intervention. In addition, the pedometer will be used to directly measure PA as a secondary outcome in both arms in the following ways: In those randomized to the intervention arm and already using the pedometer, we will average daily step count over the 14 days that follow the clinic visit at months 3 and 6. For those in the usual care group, persons will be sent home from the clinic visit at months 3 and 6 with a pedometer to wear for 14 days and return by postage-paid mailer. For step count collection at month 9 subjects in the control arm will receive a pedometer by postage mail or in person to wear for 14 days and return by prepaid mailer. At the 9-month follow up visit for the subjects assigned to the control arm, the pedometer face will be covered by a sticker to prevent feedback that may affect participant walking behavior. Intervention subjects will continue to wear the Fitbit Zip through the 9-month study time point. Clinic visits will be structured so that unblinded staff will oversee pedometer-related tasks, such as distributing the pedometers and replacing batteries. Following best practices for reporting PA data, we *a priori* define a no-wear day as one with < 200 steps, and nonadherence with step-count monitoring as having 8 or more (of 14) no-wear days (45,78). These definitions will be applied identically to both arms. These restrictions will ensure that the average step counts used in the analyses represent typical walking over 14 days of the monitoring periods.

In the secondary analyses of daily step count, we will compare the number of no-wear days and the number of participants nonadherent with monitoring between arms. Nonadherence with step-count monitoring, which is different from treatment fidelity, will not affect the primary aim of the study to examine the efficacy of WEB to increase exercise capacity, as indicated by 6MWT distance.

**f. Assessment of Body Composition and Bone Mineral Density (VABoston site only):** We will use a 5th generation GE Healthcare iDXA dual x-ray absorptiometry (DXA) scanner with enCore configuration version 12.3 to determine BMD, to assess total body composition, and

perform regional fat and lean mass analyses. As part of the study, participants will have DXA scans performed at baseline and approximately 12 months from baseline. For BMD assessment, scanning will be performed at the hip, the distal radius, and the spine. Regions with evidence of heterotopic ossification will be excluded from analyses since this will interfere with the accurate determination of BMD. Additionally, subjects will be asked to complete a body fat reading using the Omron Fat Loss Monitor (model HBF-306CN) for comparison of body fat measurement with the DXA scan, at baseline and approximately 12 months from the baseline study visit. We will exclude any subject who is pregnant or who has a pacemaker or defibrillator to minimize any potential risks.

